10.5 Follow-up Visits and Visit Window

The following follow-up visit schedule and respective visit windows will be followed for each follow-up visit ([Table 3](#)).

Table 3 Visit Window

Visit	Visit Window
Post-Procedure ¹	3-10 days post-treatment
1 Month	30 ± 7 days
3 Month	90 ± 14 days
6 Month	180 ± 14 days
9 Month	270 ± 14 days
12 Month	365 ± 28 days

1. This visit can be conducted over the phone, as long as urinalysis and MRI are not clinically indicated.

10.6 Missing Data

Variables will be summarized for all eligible subjects with available data for the majority of endpoints/data (except for the endpoints/data detailed below). Missing data in the CRF will be detected by data management and monitored via edit checks and data analysis. Follow-up to collect missing data will be conducted as outlined in the Site Management Plan.

The following imputation methods will be applied:

- When calculating the proportion of subjects with a negative in-field biopsy, subjects with missing biopsy information post-ablation will be imputed as “positive”.
- Subjects with missing pre- or post-ablation prostate volume measurements will be imputed as having a zero change in volume. In accordance with the secondary endpoint related with “change in prostate volume”, this imputation will only be performed at Month 12 Visit.
- Missing PSA data will be imputed using last observation carried forward (LOCF).

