The initial biopsy will already have been performed prior to enrollment into the study, demonstrating eligibility for inclusion. The process by which the specified distribution of lesions will be verified will be with transperineal or transrectal fusion targeted biopsy of lesion plus 10-14 core systematic biopsy to include adequate sampling of peripheral zone. Three-dimensional data on the location and specific grade for each lesion will be available and focal ablation planning will be based on this information. PSA for inclusion in the study is to have been performed prior to the initial biopsy, or it may be performed after biopsy as long as it is taken greater than 30 days after biopsy.

See **Appendix A – Standard Operating Procedure: 2. Transperineal and Transrectal Prostate Biopsies Protocol** for full details.

3.3 *Objectives*

3.3.1 *Primary Objectives*

- To determine the NanoKnife System's ablation effectiveness by measuring the negative in-field biopsy rate at 12 months.
- To determine the NanoKnife System's procedural and post-procedural safety profile by evaluating adverse event incidence, type, and severity through 12 months.

3.3.2 *Secondary Objectives*

- To evaluate urinary and erectile function after NanoKnife System treatment using validated subject questionnaires (UCLA-EPIC, IPSS, IPSS-QOL, IIEF-15).
- To determine post-NanoKnife System treatment prostate-specific antigen (PSA) kinetics, including time to PSA nadir and post-nadir PSA stability.
- To determine the change in prostate volume by comparison of prostate volume measured on multiparametric MRI (mpMRI) pre-treatment and at 12 months post-treatment.
- To determine the effectiveness of therapy by assessing the need for secondary or adjuvant treatment following therapy.
- To determine health-related quality of life (HRQoL) levels after treatment with the NanoKnife System using a validated subject questionnaire (EQ-5D).

3.4 *Hypotheses*

The primary efficacy analysis will be the rate of subjects with a negative in-field biopsy at 12 months. The rate of negative in-field biopsies will be compared to a performance goal of 0.52 using a one-sample non-inferiority test for proportions.

The null and alternative hypotheses for negative biopsy rate at 12 months are as follows:

H_0 : NanoKnife System \leq (0.61 – margin of 0.09)

H_1 : NanoKnife System $>$ (0.61 – margin of 0.09)

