4.6.1 Measure the Prostate

Volumetric analysis of the prostate will be completed during the pre-operative mpMRI as well as the 3-month and 12-month post-operative mpMRIs. The mpMRI images and volumetric analyses will be saved in the study file.

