6.4 Missing Data

The following imputation methods will be used for the primary analysis of all endpoints:

- When calculating the proportion of subjects with a negative in-field biopsy, subjects with missing biopsy information post-ablation will be imputed as “positive”
- Subjects with missing pre- or post-ablation prostate volume measurements will be imputed as having a zero change in volume
- Missing PSA data will be imputed using last observation carried forward (LOCF)
- Missing data for IIEF-5, IPSS and EPIC questionnaires will be imputed using a multiple imputation approach at the item/question level.

All other endpoints/data (e.g., safety events) will be analyzed based on available (non-imputed) data, unless specified otherwise.

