7.2 Secondary Study Objectives

- To evaluate urinary and erectile function after NanoKnife System treatment using validated subject questionnaires (University of California Los Angeles-EPIC[UCLA-EPIC] Urinary Domain [[Wei et al., 2000](#)], IPSS [[Barry et al., 1992](#)], and IPSS quality of life [IPSS-QoL] [[Rees, 2013](#)], IIEF-15 [[Rosen et al., 2002](#)]).
- To determine post-NanoKnife System treatment prostate-specific antigen (PSA) kinetics, including time to PSA nadir and post-nadir PSA stability.
- To determine the change in prostate volume by comparison of prostate volume measured on multiparametric magnetic resonance imaging (mpMRI) pre-treatment and at 12 months post-treatment.

- To determine the effectiveness of therapy by assessing the need for secondary or adjuvant treatment following therapy.
- To determine health-related quality of life (HRQoL) levels after treatment with the NanoKnife System using a validated subject questionnaire – 5-dimension scale EuroQoL (EQ-5D) ([Oppe et al., 2014](#)).

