12.7.6 Assessment of Changes in Prostate Volume Measured via mpMRI

The mean prostate volume at each visit, the overall percent reduction in prostate volume from screening to 12 month follow-up, and the proportion of subjects with reduction in prostate volume compared to screening at 12 month follow-up will be presented, as measured by mpMRI. For this assessment, our baseline will be the screening measurements.

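### Missing 12-month prostate volumes are entered as zero change with no unimputed analysis, so the reported volume reduction is scaled down by the missing fraction

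*Combined protocol and SAP*

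**What the plan says.** The objective is one of estimation. Protocol 3.3.2 puts it as: "To determine the change in prostate volume by comparison of prostate volume measured on multiparametric MRI (mpMRI) pre-treatment and at 12 months post-treatment". SAP 7.2 repeats it. Protocol 4.6.1 schedules the measurement three times: "Volumetric analysis of the prostate will be completed during the pre-operative mpMRI as well as the 3-month and 12-month post-operative mpMRIs".

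SAP 12.7.6 reports mean volume at each visit, then "the overall percent reduction in prostate volume from screening to 12 month follow-up, and the proportion of subjects with reduction in prostate volume", with screening as baseline. It names no test and no confidence interval.

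For missing values, SAP 10.6 states: "Subjects with missing pre- or post-ablation prostate volume measurements will be imputed as having a zero change in volume". It adds that "this imputation will only be performed at Month 12 Visit". Protocol 6.4 carries the same rule under the lead-in "The following imputation methods will be used for the primary analysis of all endpoints". Otherwise SAP 10.6 summarises available data for most endpoints.

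SAP 12.7.10 repeats all efficacy analyses in the per-protocol population. It adds an analysis without imputation for the primary biopsy endpoint only. Protocol 6.9 drops secondary-endpoint data collected during and after re-treatment with anything other than NanoKnife. SAP 12.1 uses data only up to re-treatment for those men, and also for men given more than one IRE re-treatment of the same lesion. Neither document says whether a volume excluded in this way counts as missing under SAP 10.6.

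**The concern.** Zero is a fixed value, not an estimate of what happened to an unmeasured prostate. Where the purpose is to estimate a change, entering zeros moves the answer toward no change by an amount that depends on follow-up rather than on the ablation.

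For the biopsy endpoint, a worst-case value has a reason: Protocol 6.2 derives the performance goal from a rate in which missing data were also counted as positive. Volume has no performance goal and no hypothesis, so a worst-case value has nothing to match. Since no planned analysis of volume change leaves the rule out, the report would contain no directly stated estimate based on measured volumes alone.

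**Working it through.** **Inputs.** From Protocol 6.2 and SAP 8.1: 100 subjects, 15% drop-out, 118 enrolled. The documents give no expected volume change, no SD and no rate of missing mpMRI. The effect sizes, the SD, the 80% below and missing fractions other than planned drop-out are therefore assumptions.

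**1. The plan's own figure.** 100 / (1 − 0.15) = 117.6, rounded up to 118, which reproduces. If the planned drop-outs have no 12-month volume, 18 of 118 are missing: m = 18/118 = 0.153 and 1 − m = 0.847.

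**2. Mean percent change.** Let d be the mean individual percent change in measured men. Then

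reported mean = [(n − k) × d + k × 0] / n = (1 − m) × d.

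| Assumed d | Reported, 18 of 118 missing |
|---|---|
| −10% | −8.5% |
| −20% | −16.9% |
| −30% | −25.4% |

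For d = −20%, the reported value is −19.0% at m = 0.05, −18.0% at m = 0.10 and −16.0% at m = 0.20. The identity is exact when percent change is averaged over men. If it is instead a ratio of mean volumes, the identity also needs similar screening volumes in measured and unmeasured men.

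**3. Proportion with a reduction.** An imputed zero enters the denominator but never the numerator, so reported proportion = (1 − m) × observed proportion. An assumed 80% becomes 0.847 × 80% = 67.8%. The ceiling is 84.7%, even if every measured prostate shrank.

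**4. Bias against the truth.** Let u be the true mean change in unmeasured men. The truth is (1 − m)d + m·u, so:

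- error of zero imputation = −m·u;
- error of the observed-case mean = m(d − u).

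If u = d = −20%, zero imputation is off by 0.153 × 20 = 3.1 points and the observed-case mean is unbiased. If u = 0, zero imputation is correct and the observed-case mean overstates the reduction by 3.1 points. The two errors are equal in size at u = d/2. The observed-case figure is the closer one whenever unmeasured men had more than half the mean reduction of measured men.

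**5. Spread.** The imputed variance is approximately (1 − m)SD² + m(1 − m)d². With an assumed SD of 15 points and 18 missing:

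| d | SE, observed | SE, with zeros |
|---|---|---|
| −10% | 1.50 | 1.31 |
| −20% | 1.50 | 1.43 |
| −30% | 1.50 | 1.61 |

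The SE is too small when the mean is below √[(2 − m)/(1 − m)²] = √(1.847/0.718) ≈ 1.6 SDs, and too large above that. The median and quartiles, which SAP 12.0 requires, also shift, because 18 identical zeros are added to the distribution.

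**The case against.** The rule is prespecified, the same in both documents, and works against the sponsor. Volume is one of eight secondary endpoints, and Protocol 6.2 says the study is not powered for claims on any of them. SAP 12.0 puts the count of missing observations in every table, so a reader could divide by (1 − m). The per-protocol set may contain fewer zeros, because Protocol 8.8 removes men who miss three consecutive visits.

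Most of this stands and limits the weight of the point. Two parts stand only partly. The SAP does not say whether an imputed man is still counted as missing, and dividing by (1 − m) cannot recover the median or quartiles. The per-protocol repeat keeps the rule for the men who remain.

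A reader might draw stronger conclusions that the documents do not support:

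- That the endpoint fails its objective. At planned drop-out a 20% reduction still reads as about 17%, in the same direction, and the effect vanishes with complete data.
- That confidence intervals for volume will have poor coverage. SAP 12.7.6 plans none.
- That precision is always overstated. Step 5 shows it can go either way.
- That the 3-month volume is ignored. SAP 12.7.6 reports mean volume at each visit; it is only not used to inform a missing Month 12 value.
- That a man who had a radical prostatectomy is entered as an unchanged prostate. Excluding data after re-treatment is stated; converting the exclusion to zero is not. This is an ambiguity to resolve.

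**Conclusion.** The point holds in limited form. Every 12-month volume change that is missing is entered as zero, and no planned analysis of volume change avoids this. Reported mean percent change and proportion reduced equal (1 − m) times the observed-case values, a relative reduction of about 15% at planned drop-out.

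Reading that as bias of the same size assumes that unmeasured men changed, on average, like measured men; the absolute sizes rest on assumed effects. If volumes excluded after re-treatment are also set to zero, m would exceed the fraction due to loss to follow-up alone.

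The endpoint is secondary, descriptive and unpowered, and the primary endpoint is unaffected. Severity is minor to moderate: a cheap improvement.

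**What to change.** In SAP 10.6 and 12.7.6:

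- Report the observed 12-month percent change, and the proportion with a reduction, among men with both volumes, with n, as the volume estimate.
- Keep zero-change imputation as a labelled conservative sensitivity analysis.
- State whether volumes excluded after non-NanoKnife re-treatment, or after a second IRE re-treatment of the same lesion, are omitted or set to zero.
- List the departure from Protocol 6.4 in SAP 6.1.

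A repeated-measures model using the screening, 3-month and 12-month volumes is optional.

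The cost is SAP wording and a table row, with no new data, and it follows the SAP's own available-data default. The downside is that the headline volume figure is no longer the worst-case one and relies on measured men being representative; the sensitivity analysis keeps the worst case in view.

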10.6.1 Imputation of Missing or Partial Dates

Partial or missing dates will be imputed only for adverse events, concomitant medication, and other dates required for analysis (e.g., Time to PSA nadir [months] is calculated as [date of PSA nadir– NanoKnife System Treatment date + 1]/30.25). For the purpose of date imputation, Visit 8 (i.e., 12 Months) is defined as the last available visit date. E.g., for PSA nadir, subjects who are not observed to have encountered the event at end of study are censored at date of last observation. In listings original (non-imputed) dates will be presented.

The following rules will be applied to impute missing or partial dates in appropriate data types:

Parameter	Missing	Additional Conditions	Imputation
Start date	D	M and Y of the event date are the same as M and Y of first NanoKnife treatment	Day of first NanoKnife treatment
		Y of the event date is before Y of first NanoKnife treatment and M of the event date is before M of first NanoKnife treatment	Last day of the month
		Y of the event date is before Y of first NanoKnife treatment but M of the event date is after M of first NanoKnife treatment	First day of month
		Y of the event date is after or the same as Y of first NanoKnife treatment but M of the event date is before M of first NanoKnife treatment	Last day of the month
		Y of the event date is after or the same as Y of first NanoKnife treatment and M of the event date is after M of first NanoKnife treatment	First day of the month
		Patient is not treated	First day of the month
	D and M	Y of the event date is the same as Y of first NanoKnife treatment	Day and month of NanoKnife treatment
		Y of the event date is before Y of first NanoKnife treatment	31 Dec
		Y of the event date is after Y of first NanoKnife treatment	01 Jan
		Patient was not treated	01 Jan
	M only	If D of the event date is present and M of the event date is not present, D of the event date will be treated as missing	See imputation rule for 'D and M'
	D, M, Y	None - date completely missing	Date of first NanoKnife treatment
Stop date	D	M and Y of the event date are the same as M and Y of end of study	Day of End of study
		Y of the event date is before Y of end of study and M of the event date is before M of end of study	Last day of the month
		Y of the event date is before Y of end of study but M of the event date is after M of end of study	First day of month

		Y of the event date is after or the same as Y of end of study but M of the event date is before M of end of study	Last day of the month
		Y of the event date is after or the same as Y of end of study and M of the event date is after M of end of study	First day of the month
	D and M	Y of the event date is same as Y of end of study	Day and Month of End of study
		Y of the event date is before Y of end of study	31 Dec
		Y of the event date is after Y of end of study	01 Jan
	M only	If D of the event date is present and M of the event date is not present, D of the event date will be treated as missing	See imputation rule for 'D and M'
	D, M, Y	None - date completely missing	No imputation, but assume ongoing
Note: In all cases, if an imputed start date is after a complete stop date, use the first day of the stop date month for start date. If stop date is before a complete or imputed start date, use either a) the last day of the start day month when start date is complete, or b) assign start date same as stop date when start date is imputed.			

11.0 Interim Analyses

No interim analysis is planned for this study.

12.0 Statistical Methods

All analyses will use SAS® version 9.4 or higher. Table and listing outputs will be presented using PRA standard layouts, but sponsor guidance for numbering of statistical outputs will be used.

Unless specified otherwise, categorical variables will be summarized using counts and percentages. Percentages will be rounded to one decimal place, except 100% will be displayed without any decimal places and percentages will not be displayed for zero counts. Continuous variables will be summarized using the number of observations (n), mean, and standard deviation, median, minimum, 25th, and 75th percentiles, and maximum. The median, minimum, 25th, and 75th percentiles, and maximum values will be displayed to the same level of precision as the raw data, the mean and 95% confidence intervals (CI) to a further decimal place and the standard deviation to two additional decimal places to a maximum of four. The count of missing observations will be provided in all tables for information only.

The rate of negative in-field biopsy at 12 months will be calculated as the number of subjects with negative in-field biopsy on follow-up transperineal or transrectal biopsy at 12 months, divided by the total number of subjects still in the study at 12 months. Clopper-Pearson method ([Clopper and Pearson, 1934](#)) will be used to report 95% confidence interval (CI) as per requirement. The same approach will be followed for rate of negative in-field biopsy at 12 months as defined by the Delphi consensus criterion of absence of clinically significant disease (≤ 3 mm of Gleason ≤ 6 disease in any biopsy core is insignificant) ([Postema et al., 2016](#)).

For Kaplan-Meier method, the median time to event and associated 95% CI will be provided.

All statistical tests used generally are performed with a 2-sided alpha=5%. P-values will be rounded to 3 decimal places. P-values rounded to less than 0.001 will be reported as <0.001 in tables.

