If the subject is re-biopsied, and there is a positive in-field core, this subject will be considered a failure for the primary efficacy endpoint (see Section 6.7). If the subject and the positive lesion still meet all of the inclusion criteria and none of the exclusion criteria⁴ (i.e., the lesion is an intermediate-risk lesion of Gleason 3+4 or 4+3 and all other criteria are met), the subject can be re-treated with the NanoKnife System and will continue to be followed up for the duration of the study for secondary efficacy endpoints and safety. If the subject and their treating physician decide on re-treatment with something other than the NanoKnife System, or if they no longer meet the inclusion/exclusion criteria for the study (i.e., they have a Gleason \geq 4+4 lesion and require whole-gland treatment), their post-re-treatment data will be excluded from the analysis.

Positive Early Out-of-Field Biopsy:

If the subject is re-biopsied, and there is a positive out-of-field core, this will not be considered a failure for the primary efficacy endpoint. If the subject and the new positive lesion still meet all of the inclusion criteria and none of the exclusion criteria⁵ (i.e., the new lesion is an intermediate-risk lesion of Gleason 3+4 or 4+3 and all other criteria are met), the subject can be re-treated for the new lesion with the NanoKnife System as part of the study. If the subject and their treating physician decide on re-treatment with something other than the NanoKnife System, or if they no longer meet the inclusion/exclusion criteria for the study (i.e., the new lesion is Gleason \geq 4+4 and the subject requires whole-gland treatment), they will exit the study though will continue to be followed for safety. These subjects who were re-treated with something other than the NanoKnife System for an out-of-field lesion prior to 12 months will have their post-re-treatment data excluded from the analysis.

Negative Early Biopsy:

If the subject is re-biopsied and there are no positive findings, they will continue in the study as planned, completing follow-up visits and the scheduled mpMRI and biopsy at 12 months.

If a subject is re-treated, regardless of the re-treatment selected, they should be followed up by the treating physician or their primary physician for routine urological care after the completion of the study.

Additional 'For Cause' Tests:

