6.7 Primary Effectiveness Endpoint

The primary efficacy endpoint is the rate of subjects with a negative in-field biopsy at 12 months. The number and proportion of subjects obtaining a negative in-field biopsy at 12 months will be presented, along with the 95% confidence interval of the proportion.

Subjects who are biopsied prior to 12 months (if there are positive findings on the 3-month mpMRI, if the subject is deemed to have biochemical progression, or if the treating physician deems there to be clinical suspicion) and have a positive in-field biopsy will be imputed as failures for the analysis of the primary efficacy endpoint. Note: Subjects with early positive out-of-field biopsies will not be considered failures for the primary efficacy endpoint.

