9.3.2 Intent-to-Treat (ITT) Population

The ITT population includes all subjects who were enrolled and treated with the NanoKnife System. Any subject who has a NanoKnife probe inserted will be considered treated for the ITT population. The ITT population will serve as the primary analysis set for all safety and efficacy endpoints.

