12.1 Subject Disposition

The number and percentage of subjects screened and included in each analysis set will be presented, together with the number and percentage of subjects who withdrew from the study prematurely and a

breakdown of the corresponding reasons for withdrawal. A tabulation of the number and percentage of subjects enrolled at each center will be presented.

If a subject undergoes re-treatment, one re-treatment with IRE for the same lesion will allow the subject to continue in the study. However, if there is more than one re-treatment with IRE on the same lesion or at least one re-treatment with a type of treatment other than IRE, then the subject will exit the study (data until the moment of re-treatment will be used for analysis) and will only be followed up for safety purposes.

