12.7.1 Rate of Subjects with a Negative In-field Biopsy at 12 Months

The number and proportion of subjects obtaining a negative in-field biopsy at 12 months will be presented, along with the 95% confidence interval of the proportion. Clopper-Pearson method will be used to report 95% CI.

Subjects who are biopsied prior to 12 months (if there are positive findings on the 3-month mpMRI, if the subject is deemed to have biochemical progression, or if the treating physician deems there to be clinical suspicion) and have a positive in-field biopsy will be imputed as failures for the analysis of the primary efficacy endpoint.²

The rate of negative in-field biopsies will be compared to a performance goal of 0.52 using a one-sample non-inferiority test for proportions.

The null and alternative hypotheses for negative biopsy rate at 12 months are as follows:

H₀: NanoKnife System \leq (0.61 – margin of 0.09)

H₁: NanoKnife System $>$ (0.61 – margin of 0.09).

For subjects with a positive biopsy, Gleason total score will also be detailed.

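### SAP 12.0 computes the primary and Delphi biopsy rates over subjects remaining at month 12, which conflicts with the plan's own ITT and missing-as-positive rules and can change the conclusion

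*Combined protocol and SAP*

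**What the plan says.** **The formula.** SAP 12.0 (Statistical Methods) gives the only explicit formula for the primary rate: subjects with a negative in-field biopsy at 12 months, "divided by the total number of subjects still in the study at 12 months". It applies the same approach to the Delphi-defined rate.

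**The population.** SAP 9.3.2 defines ITT as enrolled and treated subjects, where any probe insertion counts as treated and nothing depends on staying to month 12. It adds: "The ITT population will serve as the primary analysis set for all safety and efficacy endpoints". SAP 12.7 also presents efficacy for ITT.

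**Missing biopsies.** SAP 10.6 says "subjects with missing biopsy information post-ablation will be imputed as" positive when this proportion is calculated. Protocol 6.4 has the same rule, introduced by "The following imputation methods will be used for the primary analysis of all endpoints".

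**Early positives.** Under SAP 12.7.1, subjects biopsied before month 12 who "have a positive in-field biopsy will be imputed as failures for the analysis of the primary efficacy endpoint". For out-of-field findings, protocol 6.7 says: "Subjects with early positive out-of-field biopsies will not be considered failures for the primary efficacy endpoint". SAP footnote 2 repeats this.

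**Exit.** SAP 12.1 lets a subject continue after one IRE re-treatment of the same lesion. After more than one such re-treatment, or "at least one re-treatment with a type of treatment other than IRE, then the subject will exit the study". Data up to the re-treatment are still to be used. Protocol 4.6.16 says of subjects with an early out-of-field positive who have another therapy, or no longer meet the criteria, that "they will exit the study though will continue to be followed for safety".

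**The goal.** SAP 8.1 and protocol 6.2 derive 52% from a reported rate of 61%, in which missing data were imputed as positive, minus a 9-point margin.

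**The concern.** The rules place the same subject in different positions. A subject with an early positive in-field biopsy who then has a non-IRE therapy is a failure under SAP 12.7.1. He exits under SAP 12.1, and so is not counted at all under the SAP 12.0 formula. A subject lost to follow-up without a biopsy is positive under SAP 10.6 and absent under SAP 12.0. For anyone who has left the study, imputing a missing biopsy as positive has no effect unless that subject is in the denominator.

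SAP 6.1 (Changes from Protocol) does not list this denominator as a change, and nothing states which section takes precedence. In a single-arm pivotal study judged against a fixed goal, the success decision could then depend on which section is programmed. Removing non-negative subjects from the denominator can only raise the rate, and the goal was built on the stricter counting.

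**Working it through.** **Inputs from the documents.** Goal 0.52 (= 0.61 − 0.09), assumed rate 0.69, 118 subjects, 15% drop-out, Clopper-Pearson 95% CI, and tests generally at two-sided 5% (SAP 8.1, 12.0, 12.7.1).

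**Assumptions.** All 118 are treated, no leaver has a negative biopsy, and the count of negatives is illustrative.

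**1. The plan's own figures.** With n = ((z_α√(p0·q0) + z_β√(p1·q1))/(p1 − p0))², p0 = 0.52, p1 = 0.69 and 80% power:
- one-sided 0.05 gives 50.75, so 51 as stated;
- one-sided 0.025 gives 64.8, so 65.

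The enrolment figure also reproduces: 100/0.85 = 117.6, so 118. The level behind N = 51 is therefore one-sided 0.05, while SAP 12.0 states two-sided 5% in general. Both are carried below.

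**2. The same 69 negatives under each rule.** 15% of 118 is 17.7, taken as 18 leavers.

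| Counting rule | Rate | 95% CI | Goal of 52% |
|---|---|---|---|
| SAP 12.0, 18 leavers | 69/100 = 69.0% | 59.0 to 77.9 | met |
| SAP 12.0, 12 leavers | 69/106 = 65.1% | 55.2 to 74.1 | met |
| SAP 12.0, 6 leavers | 69/112 = 61.6% | 51.9 to 70.6 | just missed |
| ITT, missing as positive | 69/118 = 58.5% | 49.0 to 67.5 | not met |

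The exact one-sided p-value for 69/118 against 0.52 is 0.094, so the ITT result fails at either level.

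**3. Range of counts that change the conclusion, with 18 leavers.**
- Two-sided 5%: success needs 73/118 (lower limit 52.5%) under ITT but 63/100 (lower limit 52.8%) under SAP 12.0. Any count from 63 to 72 changes the conclusion.
- One-sided 0.05: the thresholds are 71/118 and 61/100, so counts from 61 to 70 change it.

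**4. False success when the true ITT rate is exactly 0.52.** If a fraction d leaves and every leaver is non-negative, the rate among those remaining is 0.52/(1 − d). The table gives the exact binomial chance of reaching the two-sided 5% threshold.

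| d | Remaining n | Rate among remaining | Threshold | Chance of success |
|---|---|---|---|---|
| 5% | 112 | 54.7% | 70 | 5.9% |
| 10% | 106 | 57.8% | 66 | 20.2% |
| 15% | 100 | 61.2% | 63 | 39.6% |

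Letting the number of leavers vary at random gives about 7%, 19% and 42%. At a nominal one-sided 0.05, again with random leavers, the figures are 13%, 29% and 54%.

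**5. The opposite assumption.** If leaving is unrelated to outcome and the underlying rate is 52%, those remaining also have a rate of 52%. The same thresholds then give 1.6%, 2.1% and 1.7% for n = 112, 106 and 100, all below 2.5%. The inflation in step 4 comes from the assumption about leavers.

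**The case against.** The strongest reply is that the documents largely show what is intended. The ITT set, the missing-as-positive rule in both documents, and the endpoint-specific SAP 12.7.1 all point to counting every treated subject. SAP 12.7.10 places the analysis without imputation among the sensitivity analyses, and even that keeps early in-field positives. On this view the SAP 12.0 sentence is a drafting slip. That is a fair reading, but SAP 12.7.1 does not state its denominator, and the only sentence that does is the conflicting one. The risk of misprogramming remains.

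Three stronger readings are tempting and are not supported:

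- **That SAP 12.0 removes all known failures.** Failures who are re-treated once with IRE, or not re-treated, stay in the study and in the denominator, as do subjects still in the study who lack a 12-month biopsy. Only those who exit or drop out are lost.
- **That leaving is tied to failure in general.** The documents make that link only for exits after re-treatment. The 15% is an allowance for loss to follow-up, with no stated relation to outcome.
- **That subjects who exit after an out-of-field re-treatment must be positive because they have no 12-month biopsy.** SAP 10.6 imputes when post-ablation biopsy information is missing. Under protocol 4.6.16 an early re-biopsy covers the whole prostate, so these subjects may have an in-field result. Coding them all as positive would in effect make them failures, against the sense of protocol 4.6.16 and 6.7. Equally, saying that an out-of-field positive is not a failure does not make the subject a negative. The plan leaves their counting open.

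A reader might also infer that a handful of out-of-field exits could decide the trial. For 71 negatives, removing three subjects moves the result from 71/118 (lower limit 50.7%, fail) to 71/115 (52.2%, pass) at two-sided 5%. But 71/118 already passes at the one-sided 0.05 that reproduces N = 51, so the example depends on the level used.

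**Conclusion.** The concern holds as an internal contradiction in the SAP on the primary endpoint, carried over to the Delphi rate, and it should be corrected before database lock. It is not evidence that the plan adopted a completer analysis as its primary estimand.

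With 18 leavers, none of them negative, the two rules differ by 69.0 − 58.5 = 10.5 percentage points at 69 negatives and give opposite conclusions. At two-sided 5% the conclusion differs for any count from 63 to 72. The chance of false success of about 6%, 20% and 40% at 5%, 10% and 15% leaving is an upper scenario in which every leaver is non-negative; there is no inflation if leaving is unrelated to outcome and the underlying rate is 52%. Only the 15% drop-out comes from the plan, and the counts of negatives are illustrative. The mismatch with a goal derived under missing-as-positive does not depend on these scenarios.

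**What to change.** 1. **Replace the SAP 12.0 sentence.** Suggested content: the denominator is all ITT subjects (all PP subjects for the PP analysis). The numerator is subjects with a negative in-field 12-month biopsy and no earlier positive in-field biopsy. Subjects with missing post-ablation biopsy information, and subjects with an early positive in-field biopsy, count as positive. State that the Delphi rate uses the same denominator.
2. **Confine any reduced denominator to the SAP 12.7.10 sensitivity analysis**, which keeps early in-field positives.
3. **Reconcile protocol 4.6.16, protocol 6.7 and SAP footnote 2 with SAP 10.6.** Pre-specify, before database lock, how subjects who exit after an out-of-field re-treatment are counted: imputed as positive, or by the in-field result of their early biopsy. Run the other option as a sensitivity analysis. This is a choice of estimand for the sponsor to make and justify; it changes no treatment or exit rule.

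The cost is SAP wording and one extra analysis; SAP 6.0 already foresees a final version before database lock. The reported rate will be lower than under the SAP 12.0 formula whenever non-negative subjects leave, by about 10 points in the 15% illustration. That lower figure is the one the protocol's own rules already require.
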